4.6.6.1 Further Analyses of ADA Classification

ADA responses are further classified as transient ADA response or persistent ADA response as follows and summarized using descriptive statistics:

- Transient ADA response: ADA-positive result detected
 - a) At only one post-baseline sampling timepoint (excluding last timepoint), OR
 - b) At 2 or more time points during treatment where the first and last ADA-positive samples are separated by a period <16 weeks, irrespective of any negative samples in between
- Persistent ADA response: ADA-positive result detected
 - a) At the last post-baseline sampling timepoint, OR
 - b) At 2 or more time points during treatment where the first and last ADA-positive samples are separated by a period ≥16 weeks, irrespective of any negative samples in between.

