### 3.1.1 Double-Blind Period

During the DB treatment period, patients will be randomized in a 1:1 ratio to receive either 120 mg or 180 mg satralizumab, as determined on the basis of body weight (Group A), or placebo (Group B) for 24 weeks (see Figure 1). Randomization will be stratified based on the following:

- Baseline SOC treatment: AChEI monotherapy and/or an OCS versus a steroidsparing IST monotherapy or a combination of a steroid-sparing IST with other treatments (an AChEI and/or an OCS)
- Autoantibody type: AChR antibody-positive versus AChR antibody-negative (includes MuSK antibody- or LRP4 antibody-positive)
- Region: North America versus Europe versus rest of world.

Blinded study drug will be administered subcutaneously to patients at Weeks 0, 2, 4, and Q4W thereafter until the end of the DB period in addition to background treatments at a stable dose (see Section 4.1.1).

An interim analysis of pharmacokinetic (PK) data was performed when approximately 30 patients completed a minimum of 8 weeks of DB treatment (including approximately 15 patients from the satralizumab group). The purpose of the interim analysis was to confirm that the achieved exposure to satralizumab (and predicted RO) was within the target range. The background therapies permitted in this study are AChEl alone or the following therapies (with or without AChEl): OCSs, one IST, and an OCS in combination with one IST. Patients should remain on stable dose of background therapy throughout the DB period and until Week 12 of the OLE, with the exception of the last AChEl dose taken prior to in-clinic visits. AChEls should not be taken for 10 hours prior to completion of efficacy assessments at each study visit (except screening visit), including QMG and MGC testing, if medically safe to do so. The permitted IST drugs are azathioprine, mycophenolate mofetil, tacrolimus, and cyclosporin A (see Section 4.4.1).

Following the interim analysis of PK data, the iDMC recommended that the initially proposed doses (120 mg  $\leq$  100 kg > 180 mg) should be retained and that the Sponsor should continue the study without dose modification. Further details on the interim analysis of PK data are provided in Section 6.11.2.

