## 3.4.10 Rationale for PK Sample Collection Schedule

Samples to assess serum concentration of satralizumab will be taken prior to each administration during the DB period, and up to Week 24 of the OLE, followed by every 12 weeks for the remaining duration of treatment to explore the pharmacokinetics of satralizumab in the gMG population following longer term treatment. This assessment will include the impact of a range of covariates on exposure (e.g., gender, race, age, and body weight), and relationships between exposure and PD, efficacy, immunogenicity, and safety endpoints.

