1.2 STUDY DESIGN

[figure not shown]
Study WN42636 has the following characteristics:

- 1. **Type/Design**: Phase 3, randomized, double-blind (DB), placebo-controlled, multicenter study. The randomization ratio is 1:1. Randomization will be stratified based on the following factors:
 - Baseline standard of care (SOC) treatment:
 - Acetylcholinesterase (AChEI) monotherapy and/or an oral corticosteroid (OCS)
 - A steroid-sparing immunosuppressant (IST) monotherapy or a combination of a steroid-sparing IST with other treatments (an AChEI and/or an OCS)
 - Auto-antibody type:
 - Acetylcholine receptor (AChR) antibody-positive
 - AChR-antibody-negative, which are either muscle-specific kinase (MuSK) antibody- or low-density lipoprotein receptor-related protein 4 (LRP4) antibody-positive.
 - Region:
 - North America
 - Europe
 - Rest of world
- 2. **Population:** Participants must fulfill the following selected inclusion criteria to be eligible for recruitment into the study:
 - Age ≥12
 - Confirmed diagnosis of gMG:
 - Documented history of myasthenic weakness
 - Myasthenia gravis (MG) severity of Myasthenia Gravis Foundation of America Class II, III, or IV at screening
 - The confirmation of the diagnosis has to be documented and supported by positive serologic test for one of the three antibody types: anti-AChR, anti-MuSK or anti-LRP4 at screening
 - A total Myasthenia Gravis Activities of Daily Living (MG-ADL) score of ≥5 at screening with more than 50% of this score attributed to non-ocular items
 - Ongoing gMG treatment at a stable dose (for precise listing refer to the Study Protocol)
 - Female participants with childbearing potential agree to remain abstinent
- 3. **Duration:** The study will include a 28-day screening period, a 24-week DB treatment period, and approximately 2 years OLE period after the last participant initiates open-label treatment.

- 4. **Dosing of blinded study drug:** Blinded study drug will be administered subcutaneously to participants at Weeks 0, 2, 4, and every four weeks (Q4W) thereafter until the end of the DB period in addition to background treatments at a stable dose (see the Study Protocol, Section 4.3). The dosing regimen proposed for this study is 120 mg Q4W for participants ≤100 kg, and 180 mg Q4W for participants >100 kg.

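### The transient and persistent ADA definitions in SAP 4.6.6.1 overlap when the final sample is positive and the first positive came less than 16 weeks earlier; no precedence rule is given

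*SAP*

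**What the plan says.** SAP 4.6.6.1 states: "ADA responses are further classified as transient ADA response or persistent ADA response as follows and summarized using descriptive statistics". Each category then has two alternative rules.

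- Transient (a): "At only one post-baseline sampling timepoint (excluding last timepoint), OR"
- Transient (b): "At 2 or more time points during treatment where the first and last ADA-positive samples are separated by a period <16 weeks", whether or not negative samples lie in between.
- Persistent (a): "At the last post-baseline sampling timepoint, OR"
- Persistent (b): "At 2 or more time points during treatment where the first and last ADA-positive samples are separated by a period ≥16 weeks", again disregarding negatives in between.

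The section does not say which category applies when both are met, or whether open-label extension (OLE) samples count. Protocol 6.7 defines ADA-positive and ADA-negative but makes no transient/persistent split, so it settles neither question.

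**The concern.** The lead-in presents a choice between two labels, so a reader will expect the two counts to add up to the ADA-positive total. Transient (a) protects that by leaving out the final timepoint. Transient (b) has no such exclusion, while persistent (a) captures every positive final sample regardless of span. The outcome is incoherent: one positive, at the final sample only, is persistent alone, whereas positives at the last two samples, which are stronger evidence of persistence, also qualify as transient.

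At stake is the meaning of a reported category. Tallied literally, the two counts can exceed the total. If a programmer forces one label, the result depends on which rule is coded first.

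**Working it through.** The plan gives no figure to reproduce here, so the check applies the four rules literally to every possible sequence of results.

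**Inputs.**
- The double-blind phase is "a 24-week DB treatment period" (SAP 1.2).
- Dosing: "Blinded study drug will be administered subcutaneously to patients at Weeks 0, 2, 4, and Q4W thereafter until the end of the DB period" (Protocol 3.1.1).
- Sampling: "Samples to assess serum concentration of satralizumab will be taken prior to each administration during the DB period" (Protocol 3.4.10). Protocol 3.4.12 takes ADA samples alongside PK samples, and Appendix 1 adds Week 24.
- Post-baseline ADA samples therefore fall at Weeks 2, 4, 8, 12, 16, 20 and 24.
- The Week 24 sample is taken before the first OLE dose and four weeks after the Week 20 dose, so it is treated here as falling during treatment.

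**Number of patterns.** Seven samples give 2^7 − 1 = 127 patterns with at least one positive.

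**Week 24 negative (2^6 − 1 = 63 patterns).** Persistent (b) needs a span of at least 16 weeks, which only Weeks 2 to 20 (18 weeks) and Weeks 4 to 20 (16 weeks) provide. With the samples in between free to vary, that is 2^4 + 2^3 = 24 patterns. The other 63 − 24 = 39 are transient only.

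**Week 24 positive (2^6 = 64 patterns).** All meet persistent (a). Those that also meet transient (b) are:

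| First positive | Span to Week 24 | Patterns |
|---|---|---|
| Week 12 | 24 − 12 = 12 weeks | 2^2 = 4 |
| Week 16 | 24 − 16 = 8 weeks | 2^1 = 2 |
| Week 20 | 24 − 20 = 4 weeks | 1 |

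That makes 4 + 2 + 1 = 7 in both categories and 64 − 7 = 57 persistent only. ADA seen only at Week 24 is persistent only, because transient (a) excludes it.

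**Totals as written.** Transient only 39; persistent only 24 + 57 = 81; both 7; neither 0. Tallied literally, transient is 39 + 7 = 46 and persistent 81 + 7 = 88, together 134 against 127. With one forced label the split is 46/81 if transient is tested first and 39/88 if persistent is tested first.

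**Visit windows.** Appendix 1 allows ±7 days at these visits. Onset at nominal Week 8 can then span as little as (161 − 63)/7 = 14 weeks, so it can also fall in both. Onset at Week 12 spans at most (175 − 77)/7 = 14 weeks, so it always stays below 16.

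**Early last sample.** If follow-up ends early and the last sample still counts as during treatment, the share in both is 1 of 3 patterns (last sample Week 4), 3 of 7 (Week 8), 7 of 15 (Week 12), 15 of 31 (Week 16) and 7 of 63 (Week 20).

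**OLE samples included.** With follow-up to OLE Week 24 (study Week 48), 7 patterns still fall in both: first positive at study Week 36, 40 or 44 and positive at Week 48. Later ADA sampling is every 12 weeks (Protocol Appendices 2 and 3), so a first-ever pair of positives at the end of the record nominally spans 12 weeks and again meets both definitions.

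**The case against.** The intent is readable. The lead-in offers one label or the other, transient (a) excludes the final timepoint, and persistent (a) has no condition beyond a positive final sample. A programmer who applies persistent first gets a clean partition. This stands as far as it goes: the defect is a missing exclusion or precedence statement, not a demonstrated miscount. A reader might infer that transient ADA will be overstated in the report, but no table layout is shown and the documents do not establish that.

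A reader might also take the affected group to be ADA arising at Weeks 12 to 20 and still present at Week 24. The SAP does not cut the classification there. Sampling continues in the OLE, SAP Table 2 speaks of ADA incidence during the study, and Protocol 4.2.2 leaves post-baseline placebo samples unassayed except on request, so any classification of those participants once on active drug would rest on OLE samples. If OLE samples count, ADA first seen at Week 12, 16 or 20 that stays positive reaches a 16-week span at OLE Week 4, 8 or 12 and becomes persistent only. The overlap then moves to the end of each participant's record; it does not disappear.

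A third inference is that the group must be sizeable because Protocol 1.4 reports ADA in 41% and 71% of satralizumab-treated patients in earlier studies. Those are any-ADA rates in another disease, with about two years' median exposure. They say nothing about onset relative to the last sample.

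Finally, no test or estimand uses the split, and SAP 4.6.6 summarizes pharmacodynamics and safety by ADA-positive or ADA-negative status only. That is correct and limits the consequence.

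**Conclusion.** The rules as written are not mutually exclusive. Anyone with at least two positives, the first less than 16 weeks before a positive final post-baseline sample, meets both transient (b) and persistent (a), and neither document says which prevails. On nominal double-blind visits, assuming the classification stops at Week 24, this is onset at Week 12, 16 or 20 with a positive at Week 24. If OLE samples count, it is onset less than 16 weeks before the last available sample. Early discontinuers can be affected in either case.

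The pattern counts show logical overlap and are not probabilities. The documents give no onset-time distribution, so the number of participants affected cannot be computed. The effect is confined to descriptive immunogenicity tables; alpha, power and the efficacy results are untouched. It is a minor point, worth correcting because the correction is so small.

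**What to change.** Do one of the following in SAP 4.6.6.1:

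- Add to transient (b): *and the last post-baseline sampling timepoint does not meet the ADA-positive (treatment-induced or treatment-enhanced) criterion*.
- State that a participant who meets any persistent criterion is classified as persistent only.

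On the positive/negative patterns above, either change gives 39 transient, 88 persistent, 0 in both and 0 unclassified.

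The clause should not simply require a negative final sample. SAP 4.6.6 counts a baseline-positive participant as ADA-positive after a 4-fold titer rise. If the rules refer to such enhanced results, a participant whose titer rises and then returns to baseline is still assay-positive at the end, and a bare negativity requirement would leave that participant in neither category.

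Also state whether the classification uses double-blind samples only or all samples to the cut-off. The cost is one clause and one sentence in the SAP, with no change to data collection.

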4.6.6.1.1 Pharmacodynamic Analyses

Serum interleukin-6 (IL-6) and soluble interleukin-6 receptor (sIL-6R) levels will be summarized by treatment group (and by dose, if the iDMC concludes that dose levels should be increased) and timepoint graphically and descriptively, as appropriate.

4.6.7 Analyses of China Subpopulation

The China subpopulation will include all participants enrolled at National Medical Products Administration-recognized sites. Results from these analyses will be summarized in a separate Clinical Study Report.

4.7 INTERIM ANALYSES

4.7.1 Safety Review

Periodic reviews of the safety data will be conducted by an iDCC with the results reviewed by the iDMC on an approximately 3-monthly basis until the last participant has completed the DB period.

4.7.2 Optional Interim for Futility

To adapt to information that may emerge during the course of this study, the Sponsor may choose to conduct one interim analysis for futility. Below are the specifications in place to ensure the study continues to meet the highest standards of integrity when an optional interim analysis is executed.

The study will not be stopped for positive efficacy as a result of the interim analysis.

An interim for futility using a threshold at a confidential cutoff value specified in a separate interim SAP was conducted on the 24 July 2023 and the iDMC confirmed no modification to the study.

4.7.3 Pharmacokinetic Interim Analysis

An interim analysis of PK data will be performed when approximately 30 participants (to include approximately 15 participants from the satralizumab group), have completed a minimum of 8 weeks of DB treatment. The purpose of the interim analysis is to confirm that the achieved exposure to satralizumab (and predicted trough receptor occupancy at steady-state [RO_{tr,ss}]) is within the predicted range. Participants with gMG with body weights representative of the overall gMG population, both in terms of range and approximate proportion, are expected to be included in the PK interim analysis dataset. The Sponsor may decide to postpone the conduct of the PK interim analysis to allow for inclusion of adolescent participants in the PK interim analysis.

A dose decision framework (including a pre-specified alternative higher dose, in case exposures are lower than predicted) will be defined in an analysis plan prior to study start (PK interim analysis plan). This plan will set out the criteria for predicted exposure and RO under which the decision for an adapted dose will be made. Predictions for exposure and RO in gMG using both the initial and pre-defined higher doses will be made using the existing popPK model, and the regimen that more closely achieves the target exposure and RO will be recommended by the iDMC.

This interim PK analysis will be performed by an external CRO while the Sponsor, participants, and investigators will remain blinded. The review by the external CRO will be restricted to PK and ADA data only, not safety or efficacy data, and no information that would reveal individual treatment assignments will be shared with the Sponsor. The external CRO will perform blinded simulations for exposure and RO, which will be made available to the iDMC, and will collaborate with the iDMC, such that the iDMC can make a dose recommendation on the basis of these simulations. Following this review, the iDMC will communicate its recommendation to the Sponsor.

Study recruitment will continue during the review period. Should a dose change be warranted, any participants treated at the original dose level will continue in the study on randomized treatment at the revised dose level, but will not contribute to the primary analysis. Additional participants will be recruited to ensure that the number of participants eligible for inclusion in the primary analysis reaches the target sample size. No type I error multiplicity correction will be performed as only PK data, unrelated to efficacy outcome, will be used for interim decision-making.

The PK interim took place on the 2 September 2022 and the iDMC recommended to continue the study without dose modification.

5. SUPPORTING DOCUMENTATION

This section is not applicable since there are no additional supporting documents.

APPENDIX 1: CHANGES TO PROTOCOL-PLANNED ANALYSES

This SAP clarifies the main analysis mentioned in the protocol with regards to the imputation strategy. The protocol applies an MMRM directly for the final analysis. In this SAP the final analysis is split into two transparent steps: Imputation and estimation of the treatment effect. The imputation uses an MMRM and the treatment effect is estimated through an ANCOVA.

